5. STUDY DESIGN

The objective of the RESPOND-AF study is to evaluate the feasibility of delivering “as-required” oral anticoagulation (OAC) guided by continuous rhythm monitoring with an implantable cardiac monitor (LINQ II™ ICM) and automated patient smartphone alerts, and to assess if this approach reduces OAC utilisation.

This study will recruit 50 participants with current paroxysmal or persistent AF being treated with a rhythm control strategy and infrequent AF episodes. The study consists of two main phases: (1) the active run-in period, which lasts one month, and (2) the treatment period which will last a minimum of 12 months.

All potentially eligible participants will undergo an enrolment visit (Visit 1) and, if they fulfil all the eligibility requirements, they will enter the active run-in period and will have a LINQ II™ ICM implant as a Day Case Procedure. A 3-month supply of their previously prescribed oral anticoagulant will be issued.

During the run-in period, participants will continue to take OAC for 30 days. Day 30 will be the start of the treatment period and the participant will be contacted by the research team. If participants meet the discontinuation criteria, they will be asked to stop OAC, otherwise they will remain on OAC until discontinuation criteria (freedom from AF episodes longer than 1 hour and/or daily burden of more than 1 hour for 30 consecutive days) are met. The purpose of the run-in period is to ensure that patients do not discontinue their pre-study OAC prematurely, i.e., less than 30 days after their last significant AF episode.

[figure not shown]

Figure 3. Study flow chart

In the treatment period patients will only be taking daily OAC if there has been an AF episode in the previous 30 days. If the LINQ II™ ICM detects an episode of AF meeting the initiation of OAC criteria,

it will send an alert to the CareLink™ Network. Our software programme actively screens Carelink every 5 minutes and will generate a patient SMS text message in response to an AF episode. The SMS is sent to the participant advising of the episode, prompting them to restart OAC. They must respond to the notification to acknowledge receipt and confirm they have commenced their OAC. The software will also send an email notification to the research team that the threshold for OAC initiation has been met. If there is no response from the patient within 24 hours, they will receive a second notification. If they do not respond to this second notification, a member of the research team will make direct contact with the patient (within 48 hours of AF episode onset) to ensure they have commenced their OAC and troubleshoot any issues they may be having.

A member of the research team will adjudicate all alerts and contact participants within 48 hours. If the alert was appropriate, participants will be advised to continue OAC for at least 30 days. If, after reviewing the episode, the alert is deemed inappropriate (false positive alert i.e., did not meet criteria for OAC initiation) participants will be instructed to stop OAC and this false positive alert will be logged.

Once OAC is initiated, participants may discontinue OAC if they have 30-day freedom from: 1) any continuous AF episode longer than 60 minutes, and 2) any AF burden of more than 1 hour in a 24-hour period. A member of the research team will contact them by telephone to do so.

[figure not shown]

Figure 4. Study algorithm for the initiation and discontinuation of oral anticoagulation (OAC)

As a safety measure, the LINQ II™ ICMs perform automatic transmissions every 24 hours to CareLink™. The research team will conduct a daily review of all transmissions. If an AF episode/AF burden is identified that meets initiation criteria but failed to trigger an appropriate smartphone alert, participants will be contacted within 24 hours and instructed to restart OAC. Any failure of the system to generate an alert will be reviewed and logged.

During the study (run-in and treatment period), participants will keep a diary of any new drugs started, stopped or dose changes.

At the end of the study, participants will be invited to attend the Device Clinic for a final manual device interrogation and full clinical review of their medical care over the previous 12 months (Visit 2). They may choose to have the LINQ II™ ICM explanted during the final visit or leave it in-situ. It can be deactivated or else continue to monitor the patient’s heart rhythm. The primary endpoint is total OAC utilisation which will be calculated by dividing the number of days on OAC by the total number of days during the treatment period.

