	
attacks (TIA) and systemic embolism)
 
2. Major bleeding
 
3. Minor bleeding
 
4. Any stroke (ischaemic, haemorrhagic or undermined)
 
5. All-cause mortality
 
6. Protocol adherence
 
7. To assess response time from AF episode onset to patient starting as-required OAC
	
patients on as-required OAC
 
2. Calculate the rate of major bleeding in patients on as-required OAC
 
3. Calculate the rate of minor bleeding in patients on as-required OAC
 
4. Calculate the stroke rate (ischaemic, haemorrhagic or undetermined)
 
5. Calculate the rate of all-cause mortality in patients on as-required OAC
 
6. Calculate the percentage of daily automatic transmissions and percentage of patients that restart OAC within 24 hours of the smartphone-alert.
 
7. Time from AF episode onset to detection, time to alerts being sent and acknowledged and OAC being taken by the participant. Proportion of missed AF episodes, transmissions or alerts.
	
2. During follow-up (minimum 13 months)
 
3. During follow-up (minimum 13 months)
 
4. During follow-up (minimum 13 months)
 
5. During follow-up (minimum 13 months)
 
6. During follow-up (minimum 13 months)
 
7. During follow-up (minimum 13 months)

Intervention(s)	
As-required oral anticoagulation (OAC):
 
 • Initiate OAC if continuous AF episodes longer than 1 hour or total AF burden of more than 60 minutes (>4.2%) over a 24-hour period. 
 ○ Dabigatran ○ Rivaroxaban ○ Apixaban 		

	
○ Edoxaban• Discontinue OAC if freedom over a consecutive 30-day period from: (1) AF episodes longer than 1 hour, and (2) AF burden more than 60 minutes in any 24-hour period.
--	--

CONFIDENTIAL

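### The instruction to stop OAC after a false-positive alert does not depend on current OAC status, and for participants already on OAC it conflicts with the 30-day discontinuation criteria

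*Protocol*

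**What the plan says.** Section 5 (Study Design) describes the alert procedure for the treatment period. The research team adjudicates every alert and contacts the participant within 48 hours. There are two outcomes:

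- Appropriate alert: "If the alert was appropriate, participants will be advised to continue OAC for at least 30 days".
- Inappropriate alert: "participants will be instructed to stop OAC and this false positive alert will be logged". The section explains what makes an alert inappropriate in these words: "false positive alert i.e., did not meet criteria for OAC initiation".

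The next paragraph of Section 5 gives the discontinuation rule: "Once OAC is initiated, participants may discontinue OAC if they have 30-day freedom from" long AF episodes and high daily AF burden. The Synopsis has the same criterion: "Discontinue OAC if freedom over a consecutive 30-day period from" the same two events. Neither place makes an exception for a false alert.

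Section 5 also describes who may already be on OAC in the treatment period. It says "In the treatment period patients will only be taking daily OAC if there has been an AF episode in the previous 30 days". Of participants who do not qualify to stop when run-in ends, it says "otherwise they will remain on OAC until discontinuation criteria" are met. It gives the purpose of run-in as preventing participants from stopping their pre-study OAC within 30 days of their latest significant episode.

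**The concern.** The false-positive instruction is triggered by the adjudication of a single alert. As written, it does not ask why the participant is taking OAC or how long ago the last true episode was. A participant can be on OAC for a reason that has nothing to do with the false alert. That participant would be told to stop under one rule, while the discontinuation criteria in the same section are not yet met.

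Two things are at stake. The first is safety, on the protocol's own account. Section 3 cites device data in which the odds of stroke were raised seventeen-fold in the first 5 days after an AF episode and returned to baseline at 30 days. A stop inside that interval is what the 30-day rule is there to avoid. The second is how the strategy is delivered. The primary endpoint counts days on OAC. Courses ended by a false alert would reduce those days for a reason unrelated to the participant's AF, and team members could resolve the conflict in different ways.

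**Working it through.** The plan states no figure for this point, so the check sets the rules side by side for each state a participant can be in when a false alert arrives.

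| State at the false alert | False-positive instruction | 30-day criteria or other rule | Result |
|---|---|---|---|
| (a) Treatment period, off OAC, at least 30 days since the last true episode; OAC begun on this alert | Stop | Already met | Agree |
| (b) Treatment period, on OAC, fewer than 30 days since a true episode | Stop | Not yet met | Conflict |
| (c) Treatment period, on OAC, carried over from run-in without meeting the criteria | Stop | Remain on OAC until met | Conflict |
| (d) Run-in | Not stated to apply | "During the run-in period, participants will continue to take OAC for 30 days" | No contradiction shown |

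States (b) and (c) can arise only if alerts reach people who are already on OAC. Sections 5 and 6.9 tie the message to the detected AF episode or burden, not to current OAC status, and Section 5 has all alerts adjudicated. No readable text suppresses alerts during an OAC course. In state (c), OAC was continued from before the treatment period, so the false alert did not start it.

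**Illustration of the size in state (b).** Inputs: a 30-day interval (Synopsis and Section 5) and adjudication 0 to 2 days after the alert (the 48-hour limit in Section 5). Assumptions: the interval is counted from the day of the true episode, no further true episode occurs in it, and the treatment period is 365 days (the protocol's minimum is 12 months).

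For a false alert on day d, the stop falls between day d and day d + 2. Days short of the interval run from 30 − (d + 2) = 28 − d to 30 − d.

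- d = 1: 27 to 29 days.
- d = 15: 13 to 15 days.

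As a share of that participant's treatment period, 29 / 365 = 0.079, about 7.9 percentage points of OAC utilisation. A longer treatment period makes the share smaller.

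The frequency of state (b) or (c) cannot be computed, because the protocol gives no false-positive rate for alerts.

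**The case against.** The best counter-argument is context. The text leading up to the stop instruction describes someone who is off OAC: the message prompts a restart, and the participant confirms having begun. Section 6.9 likewise speaks of initiating OAC. Read that way, the instruction simply undoes a start that should not have happened, which is state (a), where nothing conflicts. Figure 4, the algorithm for starting and stopping OAC, is not shown and could contain a branch on current OAC status. A team member also reviews each alert and would often notice a recent true episode.

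Much of this stands. It makes unqualified wording more likely than a deliberate rule. It does not remove the conflict: the prose has no such limit, adjudication is described in terms of the alerted episode, and the prose would still have to agree with any branch in the figure. The daily transmission review in Section 5 is described as looking for qualifying AF that did not trigger a proper alert, so it is not aimed at this situation.

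A reader might infer several stronger points that the document does not support:

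- **A contradiction in run-in.** The alert procedure is introduced as part of the treatment period, Section 6.10 starts the alert-guided regimen after run-in, and run-in has its own instruction to continue.
- **A flat ban on stopping before 30 days.** The general rule in Section 5 is permissive: participants may stop if the criteria are met. The stricter wording concerns those carried over from run-in.
- **A frequency taken from the Section 3 forecast.** The forecast reductions of 86.5% and 46.3% imply 13.5% and 53.7% of time on OAC. Even if alerts came at random, these would be shares of false alerts and not event rates, and they come from a retrospective cohort with complex cardiac devices, whereas this trial selects infrequent AF.
- **A biased endpoint.** A day truly off OAC is correctly counted as off. The issue is how the strategy is delivered, not how it is measured.

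**Conclusion.** The point holds for one part of the protocol. In the treatment period, for a participant already on OAC within 30 days of a true qualifying episode, or carried over from run-in without meeting the criteria, the false-positive instruction in Section 5 conflicts with the 30-day criteria in the Synopsis and Section 5 and with the stated aim of the run-in. Elsewhere the rules agree or no contradiction is shown.

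The effect on an affected participant could be material, but how often it would occur is unknown. The day counts rest on the assumptions listed with them, and day 1 is close to the extreme: a false alert midway through the interval costs about half as much. The conclusion also rests on the readable prose, since the algorithm figures are not shown. Because the text is an instruction to stop anticoagulation and the repair is small, it should be put right. This review takes no position on which clinical rule should prevail.

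**What to change.** Reconcile the false-positive instruction in Section 5 with the 30-day discontinuation criteria in the Synopsis and Section 5. Add one sentence stating which of them governs when an inappropriate alert occurs while OAC is already being taken for an earlier reason. Check Figure 4 against that sentence and amend it if it differs. The choice of rule belongs to the investigators.

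The cost is one sentence and possibly one change to a figure. No sample size or analysis is affected. Recording OAC status in the log of false-positive alerts would make affected days easier to identify. This is optional, because the medication diary and the time-stamped replies may already allow it to be derived.

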5.1 Study Timeline

This 24-month prospective single centre feasibility study is to be conducted in 2 phases:

1. Patient recruitment, ICM implant and data entry (20 months): during this period recruitment will take place and the LINQ II™ ICM will be implanted at the start of the active run-in period for 1 month. They will then enter the treatment period for a minimum of 12 months. Data entry to be completed within 6 weeks of enrolment and will be monitored every 2 months.
- 2.
3. Completion of data entry and analysis (4 months): to finalise the data entry, adjudicate all AF episodes and perform the statistical analysis. A final wrap up meeting will be convened at the end of the study with all key investigative staff contributing to the final report and manuscript.

[figure not shown]

Figure 5. Study timeline.

5.2 Study Risks

The LINQ II™ ICM has CE marking and is used in routine clinical practice; the implant procedure is safe and minimally invasive. The procedure will be performed under sterile conditions and local anaesthetic using the insertion tools supplied by the manufacturer to inject the ICM under the skin in the anterior chest wall.

There are no known contraindications. Potential adverse events include:

- bruising,
- haematoma (<1%),
- superficial infection (<1%),
- keloid scar formation,
- device migration,
- device extrusion.

By taking part in this study, participants understand that the stroke prevention strategy proposed is not the standard of care in current guidelines. Although the thromboembolic and bleeding events were low in the small studies that tested the hypothesis of as-required OAC with DOACs, they were not designed to provide a definitive answer regarding safety or efficacy of this novel management strategy. The initial data is nonetheless encouraging, and we believe that in a carefully selected population with low-risk of stroke and with low AF burden an as-required approach is safe and effective at preventing AF-related strokes.

5.3 Study Benefits

The main benefit from this study will be for future patients. It is important to understand if this novel approach to OAC in AF patients is a feasible, effective, and safe. It is important to develop a robust platform that can accurately monitor and notify patients during AF episodes, paving the way for a randomised trial testing the hypothesis of “as required” oral anticoagulation.

A reliable as-required OAC strategy will offer the same thromboembolic protection as continuous OAC, whilst at the same time reducing bleeding complications, reduce oral anticoagulation requirement, and may reduce overall healthcare associated costs. Participants may experience these benefits directly while taking part in the study, as well as future patients experiencing these benefits.

Patients may benefit directly from continuous heart rhythm monitoring during the study, which may help guide better clinical management decisions of their Atrial Fibrillation (ie. it may help their clinical team make decisions on medications, cardioversion, need for permanent pacemaker implant, need for AF ablation procedure). This would not be available if they were not part of this trial. The LINQ II™ ICM may also pick up other clinically relevant arrhythmia, which would not otherwise have been known about.

6. PARTICIPANT IDENTIFICATION

6.1 Inclusion Criteria

Study participants must satisfy the following conditions:

- Participant is willing and able to give informed consent for participation in the trial.
- Understand the risk and willing to discontinue oral anticoagulation (OAC).
- Any gender aged 18 years or above.
- Non-valvular paroxysmal atrial or persistent atrial fibrillation (AF) with a current rhythm control strategy. Paroxysmal patients must have < 3 documented or symptomatic episodes of >1 hour duration in the previous 3 months. Persistent patients must have been in continuous sinus rhythm for at least 4 weeks prior to enrolment.
- CHA₂DS₂-VASc score between 1 and 3 in men and between 2 and 4 in women.
- Able to take DOAC in guideline recommended doses.
- Left atrial diameter on echocardiogram less than 5 cm (AP dimensions) or LA volume less than 48 ml/m².

6.2 Exclusion Criteria

The participant may not enter the study if ANY of the following apply:

- Any contraindication to OAC therapy with a DOAC in guideline recommended doses.
- Mechanical heart valve prosthesis or moderate-to-severe mitral valve stenosis.
- Permanent atrial fibrillation.
- Hypertrophic cardiomyopathy.
- Documented previous thromboembolic event (stroke, TIA or systemic embolism).
- Spontaneous echo contrast observed in any imaging modality.
- History of intracardiac thrombi.
- History of congenital heart disease.
- Severe chronic renal disease (eGFR <15 ml/m) or on renal replacement therapy.
- Pregnant or planning pregnancy.
- Indication for OAC other than atrial fibrillation.
- Inability to comply with protocol.
- Smartphone with OS not compatible with MyCareLink Heart™ app.
- Contraindication for implantable cardiac monitor.
- Visual or physical impairment that prevents ability to read and acknowledge smartphone/watch notifications.
- As far as is practicable, language barriers between the investigators and study participants will be circumvented using NHS interpreters. If necessary, we will arrange for smartphone alerts to be sent to participants in their native language.

6.3 Recruitment

The research team will screen the Arrhythmia Outpatient Clinics, Remote Device Clinics, AF Ablation lists and Cardioversion Lists at Oxford University Hospitals for potential participants. All members of the research team are part of the Cardiac Rhythm Management Care Team, and as such, all screened participants will be under their direct care.

A letter of invitation, a patient information sheet (PIS) and a consent form will be given to potential participants at the time of the Outpatient Clinic or posted to them later.

Patients will have the opportunity to contact the Research team if they wish to take part. A member of the Research team will also make a follow-up contact with potential participants after they have received their PIS.

Once the potential participants have considered the information and had the opportunity to have their questions addressed and speak with their family members and /or GP, if they agree to take part in the study, they will be invited for Visit 1.

During Visit 1, if participants are found to be eligible and wish to participate, they will have a Baseline Assessment performed and Informed Consent taken to enter the study. The aim is to recruit 50 patients in total.

Members of the clinical team (who are not members of the Research team) may also identify patients through their clinical practice and provide information (including a patient information leaflet) regarding the trial and put them in contact with the research team. If the participants meet the inclusion criteria, they will be invited to participate in this study and, if they agree to participate, they will undergo screening and eligibility assessment.

6.4 Informed Consent

The participant must personally sign and date the latest approved version of the Informed Consent form before any trial specific procedures are performed.

Written versions of the Participant Information Sheet and Informed Consent will be presented to the participants detailing no less than: the exact nature of the trial; what it will involve for the participant; the implications and constraints of the protocol; the known side effects and any risks involved in taking part. It will be clearly stated that the participant is free to withdraw from the trial at any time for any reason without prejudice to future care, without affecting their legal rights and with no obligation to give the reason for withdrawal.

The participant will be allowed as much time as wished to consider the information, and the opportunity to question the Investigator, their GP/Cardiologist or other independent parties to decide whether they will participate in the trial. Written informed Consent will then be obtained by means of participant dated signature and dated signature of the person who presented and obtained the Informed Consent. The person who obtained the consent must be suitably qualified and experienced and have been authorised to do so by the Chief/Principal Investigator. A copy of the signed Informed Consent will be given to the participant. The original signed form will be retained at

the trial site, kept in a marked lever arch folder, in the Cardiology Clinical Research Fellows' office, Level 2, John Radcliffe Hospital. This office is on a staff-only corridor, and the door is combination locked. Only members of the Cardiology Research team have access to this office.

6.5 Screening and Eligibility Assessment

If a participant meets the inclusion criteria they will be invited to participate in the study. After agreeing to participate and signing the consent form the following data will be collected:

1. Demographics (age, gender, ethnicity)
2. Detailed collection of medical history which should include atrial fibrillation history, previous cardiac procedure (cardiac surgery, atrial fibrillation ablation, direct current cardioversion), significant co-morbidities (including previous thromboembolic events)
3. Imaging data recorded previously as part of standard clinical practice left ventricular systolic function, diastolic function, evidence of valvular heart disease, cardiac chamber size.
4. Current medications
5. Height, weight, and BMI

